5.5.4 Lost to Follow-up Rates

The primary lost to follow-up rate will be summarized for the Day 7 follow-up. A subject will be categorized as having a Day 7 follow-up if the Date of Day 7 Follow-up is not miss-

ing (regardless if the date is within the 7-day window). If the date is missing, the subject will be categorized as missing the Day 7 follow-up. The rate of Day 7 follow-ups will be summarized as a proportion. A similar analysis will be done for the Day 21 follow-up.

For the daily assessments, we will calculate whether the subject completed at least five out of the six possible daily assessments. The proportion of subjects who completed at least five assessments will be summarized.

5.5.6 Clinic or ED Visits

Two definitions of clinic or ED visits will be derived. These are described in the following paragraphs:

Any Visit A subject will be categorized as having seen a provider if the subject indicates that they have seen a doctor (in the ED or primary care provider) since the study ED visit on the Day 7 follow-up (regardless of whether it is planned or unplanned).

Unplanned Visit A subject will be categorized as having seen a provider if the subject indicates that they have seen a doctor (in the ED or primary care provider) since the study ED visit on the Day 7 follow-up (only an unplanned study visit for a non-ED visit).

The proportions of subjects for the two definitions above will be summarized out of the proportion of subjects with a Day 7 follow-up visit (categorized as having a Day 7 follow-up if the Date of Day 7 Follow-up is not missing). A repeat of these two summaries will be performed for the Day 21 follow-up visit.

5.5.7 Hospitalization

A subject will be categorized as having been hospitalized if the subject indicates that they were hospitalized since the study ED visit on the Day 7 follow-up. The proportion of subjects who were hospitalized will be summarized out of the proportion of subjects with a Day 7 follow-up visit (categorized as having a Day 7 follow-up if the Date of Day 7 Follow-up is not missing). A repeat of this summary will be performed for the Day 21 follow-up visit.

5.5.9 Adverse Events

Adverse events will be captured through the daily assessments. On the daily log and on Day 7, we ask about several symptoms. On any daily assessment or Day 7, whatever the worst category reported across the week is the category assigned to the subject. For example, on the first day following the ED visit, if the parent reports the child had 4+ episodes of vomiting that day, then the child will be categorized as 'Severe' AEs regardless of how quickly they might improve the remaining part of the week. Allergic reactions is captured as 'rash', stomatitis is captured as 'had any ulcers in the mouth', and candidiasis is captured as 'had any white patches in the mouth or a rash in the groin region'. The categorization of mild, moderate, and severe can be seen in Figure 1.

October 5, 2021

SAP Version 1.00

CONFIDENTIAL

October 5, 2021

5.5.13 Frequency and Types of Adverse Events

For each of the adverse events summarized in Figure 1, we will categorize each subject as whether or not the AE was observed based on:

- the daily assessments
- the Day 7 survey

If the subject experiences the AE at any reported period, the subject will be labeled as having experienced the AE. If the subject has at least one assessment completed (either daily or Day 7) and all observed assessments do not indicate the AE occurring, the subject will be labeled as not experiencing the AE.

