9.3 Adverse Event Reporting

The site investigator is responsible for evaluating all adverse events at their Clinical Center and ensuring that they are properly reported. Specified adverse events that occur during this study will be recorded. The nature of each experience, date and time (where appropriate) of onset, outcome, course, and relationship to treatment will be documented. The safety profile of amoxicillin is well established, and this trial is not powered to detect new, unknown safety effects, therefore, there will be no additional AE collection outside of the daily symptom diary during this study. All serious adverse events (SAE) will be collected and recorded. The investigative team anticipates AEs, both severe and non-severe, to occur among enrolled children at a similar rate as untoward medical events occur in comparable pediatric populations outside of a research setting.

AEs that the study team expects may occur during the research include, but are not limited to: adverse reactions to amoxicillin (e.g., skin rash), progression of pneumonia-related symptoms (e.g., work of breathing), and onset of other common and uncommon childhood illnesses (e.g., diarrhea). Research staff will obtain information about side effects from scheduled follow-up contacts.

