5.2 Methods for Withdrawals, Missing Data, and Outliers

Per the intention-to-treat principle, subjects who withdraw from the study or are lost to follow-up will have all available data used in the analysis. In the event that a substantial number of subjects are withdrawn or lost to follow-up, baseline characteristics and available information on hospital course will be reviewed and compared to subjects not withdrawn or lost, to assess empirically if these subjects differ from those remaining in the study for the scheduled treatment and follow-up time.

Outliers will be reviewed for validity. Outliers that are valid, for example, high number of vomiting episodes, will be included in all primary reports from this trial.

Due to this being a pilot study, missing data will remain missing instead of being imputed.

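### The rule that one negative assessment makes a child AE-free (SAP 5.5.13) turns the solicited-AE proportion into a lower bound, and the plan neither labels it so nor shows incomplete observation by arm

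*SAP*

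**What the plan says.** SAP 5.5.13 uses the six daily assessments and the Day 7 survey to decide, for each AE in its Figure 1, whether a child had it. The positive rule is: "If the subject experiences the AE at any reported period, the subject will be labeled as having experienced the AE". The negative rule is: "If the subject has at least one assessment completed (either daily or Day 7) and all observed assessments do not indicate the AE occurring", in which case "the subject will be labeled as not experiencing the AE". Nothing in the visible text sets a minimum number of assessments for the negative label, adjusts for time observed, or provides an 'unknown' category for a child who answered once and then stopped.

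SAP 5.5.9 grades severity by the same logic: "whatever the worst category reported across the week is the category assigned to the subject".

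Three other provisions bear on this:

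- SAP 5.2 states that "missing data will remain missing instead of being imputed", and also that all available data from withdrawn or lost children are used.
- SAP 5.5.4 reports, as a follow-up measure, the share of children completing "at least five out of the six possible daily assessments". It is not linked to the AE denominator.
- Protocol 9.3 says of non-serious events that "there will be no additional AE collection outside of the daily symptom diary during this study". The SAP adds the Day 7 survey as a source.

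**The concern.** The label is a statement about the whole week, but it can rest on one day. A family that answers the first diary with no symptoms and then stops responding enters the denominator as a child without the AE, although up to six of the seven reporting windows were never observed. The worst-grade rule has the same weakness, since fewer reports can only give an equal or milder worst grade.

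The hypothesis for the large trial includes fewer adverse effects without antibiotics (Protocol, Abstract and section 1), and the pilot will summarize events by arm (Protocol 6.2). A reader planning the larger trial may take those proportions as 7-day risks. The visible SAP text does not say that loss to follow-up or diary completion will be shown by arm, so the reader could not tell how much of a low AE proportion, or of a gap between arms, reflects missing reports.

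**Working it through.** **Inputs from the documents.** SAP section 8: 2 children per site per month × 3 sites × 6 months = 36 randomized, which reproduces the plan's figure. Allocation is 1:1, so about 18 per arm. SAP 5.5.4 gives six daily assessments; with Day 7 that makes 7 reporting windows.

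**Inputs that must be assumed.** The documents give no AE risk, onset pattern or drop-out rate. The figures below are illustrations.

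**Direction.** With accurate reports, children labelled positive are a subset of those who truly had the AE. Among children with at least one assessment, the labelled proportion therefore cannot exceed the true 7-day proportion, and it is smaller whenever an AE begins after a child's last report. This does not depend on the assumed rates.

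**Size.** Let p = 0.20 be the weekly risk, with onset uniform over the 7 windows. Of 18 children, k stop after d diaries with no Day 7 contact, for reasons unrelated to AEs; the rest are fully observed.

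Expected reported proportion = [(18 − k)p + k·p·d/7] / 18

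| k | d | Expected positives | Reported | Shortfall, points | Shortfall, children |
|---|---|---|---|---|---|
| 2 | 3 | 3.20 + 0.17 = 3.37 | 18.7% | 1.3 | 0.23 |
| 4 | 2 | 2.80 + 0.23 = 3.03 | 16.8% | 3.2 | 0.57 |
| 6 | 1 | 2.40 + 0.17 = 2.57 | 14.3% | 5.7 | 1.03 |

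**Sensitivity to onset.** Let a share g stop after one assessment, with constant daily hazard, so that the first-window risk is h = 1 − (1 − p)^(1/7) = 0.0314. The reported proportion is (1 − g)p + g·h. For g = 10%, 20% and 30% it is 18.3%, 16.6% and 14.9%. If half the weekly risk falls on day 1, it is 19%, 18% and 17%: a smaller shortfall, but still one.

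**Between arms.** Take equal true risk and constant hazard, with 5% stopping after one assessment in one arm and 30% in the other. At 20% risk the reported proportions are 0.95 × 0.20 + 0.05 × 0.0314 = 19.2% and 0.70 × 0.20 + 0.30 × 0.0314 = 14.9%, a false gap of 4.2 points before rounding (0.76 of a child in 18). At 40% risk the gap is 8.2 points (1.48 children). With equal drop-out and the same risk and onset in both arms, the gap is zero.

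**Alternatives, in the table's three scenarios (in its order).**

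- Adequately observed children only, same requirement for positives and negatives: (18 − k)p / (18 − k) = 20% each time.
- Early positives kept but early negatives removed: expected positives / (18 − k + k·p·d/7), that is 3.37/16.17 = 20.8%, 3.03/14.23 = 21.3% and 2.57/12.17 = 21.1%. This leans upward.
- Upper bound, with every incomplete child counted as positive: [(18 − k)p + k] / 18, that is 5.2/18 = 28.9%, 6.8/18 = 37.8% and 8.4/18 = 46.7%.

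**The case against.** The strongest defence is that SAP 5.5.13 only applies SAP 5.2's instruction to use all available data. It classifies what was observed and fills in no missing diary, so a reader who infers a flat contradiction with the no-imputation sentence goes too far. This stands in part: the two provisions can be read together, but only if the negative label means 'not observed'. As worded, it says more than that.

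The following points also stand and limit the concern:

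- SAP 5.5.4's five-of-six figure measures diary completion; the SAP does not call it adequate observation for AEs. The Day 7 denominators in SAP 5.5.6 and 5.5.7 simply reflect the form the data come from. Neither shows that the SAP set a stricter AE standard and then broke it.
- A reader might infer that the arm with more early drop-out will look safer. Nothing in the documents indicates that drop-out will differ by arm. A family that reports an early side effect and then stops is already counted as positive; only unreported events are lost.
- A reader might infer that the rule hides every kind of adverse event. It covers the solicited AEs of Figure 1. SAEs are recorded separately from randomization through Day 21 (Protocol 9.3.3).
- SAP 2.2.4 sets no safety outcomes, Protocol 6.2 excludes inference between arms, and the Abstract promises only to show that adverse events can be collected. With 4 events in 18 the exact 95% interval is already 6% to 48%, far wider than the bias.
- Day 7 recall may cover missed diaries. The recall period, Figure 1 and parts of the exploratory text are not visible in the public copy.

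None of this removes the lower-bound property or helps a child lost before Day 7.

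**Conclusion.** The concern holds in a limited form. The solicited-AE proportion and worst grade will equal or understate what happened over the 7 days, provided reports are accurate, and nothing visible in the plan corrects or discloses this. Under the table's assumptions, which have no basis in the documents, the understatement is about 1 to 6 percentage points, or 0.2 to 1 child per arm; it is smaller if onset is early. With equal true risk and the same onset pattern, the comparison between arms is distorted only if early non-reporting differs by arm. The effect is confined to descriptive, exploratory figures that may inform the larger trial. The primary outcome, the enrollment rate, is untouched. This is a cheap improvement worth making, not a threat to the pilot.

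**What to change.** In SAP 5.5.13 and 5.5.9:

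1. Keep the present any-report proportion, label it 'AE observed / not observed', and describe it as a lower bound on the 7-day proportion.
2. Show by arm the number of children with incomplete AE observation: fewer than five of six diaries and no Day 7 contact covering the whole period since the ED visit. State the Day 7 recall period.
3. Add the proportion and worst grade among adequately observed children, with the same requirement for children with and without the AE. If those children are in effect observed for the whole week, this is unbiased when drop-out is unrelated to AEs. A child with five diaries and no Day 7 contact still has unobserved days; a time-to-first-AE estimate censored at the last assessment is the alternative that handles this.
4. If bounds are wanted, pair the lower bound in item 1 with an upper bound that counts every incomplete child without a report as having the AE.
5. Do not count positives from incompletely observed children while dropping the negatives; that gives about 21% against a true 20% in the scenarios above.

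The cost is SAP wording, one or two table rows and a slightly smaller denominator in the added line. All of it uses data already planned for collection.

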5.6 Independent Review

All statistical analyses for primary reporting of trial results will be independently verified through dual programming. Two statisticians will each program all datasets and analyses for the DSMB reports and the primary manuscript(s) and the results will be compared. This process will begin at the analysis design stage and will continue through writing of abstracts and manuscripts.

6 INTERIM ANALYSES

6.1 Frequency of and Timepoints for Interim Analysis

This is a pilot study evaluating the feasibility of the trial so no formal interim analyses will be performed. The DSMB will meet prior to study start and then once study is completed. If enrollment is anticipated to go longer than 8 months, then the DSMB will have the option to meet to perform a safety review of the data.

6.2 Stopping Rules for Interim Efficacy Analysis

There is no formal efficacy monitoring in this pilot study.

6.3 Futility Monitoring in the Interim Analysis

There is no formal futility monitoring in this pilot study.

6.4 Subgroups in the Interim Analysis

There are no formal pre-specified subgroups of interest in this pilot study that will be evaluated due to the small number of enrollments.

7 PLANNED ANALYSES

7.1 Description of Subject Characteristics

Publication of the primary results will include reporting of key baseline characteristics overall, and by assigned treatment arm. These will include, but are not limited to

- gender
- race
- age
- ethnicity

7.2 Primary Outcome Analysis

The primary outcome, enrollment rate, and the 95% confidence interval around the enrollment rate will be summarized overall.

7.3 Secondary Outcome(s) Analyses

7.3.1 Consent and drop-out rates between the two stages of consent

The consent rate between Stage I and Stage II (summarized as a proportion) and exact 95% confidence interval of the proportion will be reported.

7.3.2 Parental attitudes and beliefs about trial procedures

Parental attitudes and beliefs about trial procedures will be evaluated outside of the clinical trial. Qualitative analyses will be performed by the lead investigator and his team and details are not discussed in this SAP.

7.3.3 Feasibility and usability of video chat follow-up

The video follow-up rate and entire assessment completed through video (summarized as a proportions) and exact 95% confidence intervals of the proportions will be reported.

7.3.4 Lost to follow-up rates

Lost to follow-up rates (summarized as a proportions) and exact 95% confidence intervals of the proportions will be reported.

| | l |
|--|---|
| | |
| | |
| | |
| | |
| | |
| | |
| | |
| | |
| | |
| | |
| | |
| | |
| | |
| | |
| | |
| | |
| | |

8 SAMPLE SIZE DETERMINATION

We are seeking to enroll and randomize 2 children per site per month as part of this pilot trial. Using 40% as an estimate of children enrolled in Stage I being eligible for Stage II (PCT <0.25), we anticipate that we will need to obtain PCT and baseline data from 5 children per site per month to enroll 2 with PCT <0.25 at each site.; Thus, over a 6 month period, we anticipate obtaining baseline data and PCT on 90 children across 3 sites and enrolling 36 of these children into this pilot RCT. As soon as 36 children are enrolled in the RCT, the pilot trial will stop.

9 References
